Appendix 1 Schedule of Activities (cont.)

Study Day	Screening Period	Observational Period						Follow-Up (or Early Termination) ^a
	Days -29 to -2	Day -1 to 1 (Baseline)	Day 85 (Month 3)	Day 169 (Month 6)	Day 253 (Month 9)	Day 337 (Month 12)	Day 421 (Month 15)	
Visit Window (days)			±7	±10	±7	±10	±7	
Type of visit	CL	CL	CL	PH	CL	PH	CL	CL or PH
Adverse events ^t	x	x	x	x	x	x	x	x
Concomitant medications ^u	x	x	x	x	x	x	x	x

CL = clinic; ClinROs = clinician-reported outcomes; CSF = cerebrospinal fluid; C-SSRS = Columbia-Suicide Severity Rating Scale; eCRF = electronic Case Report Form; HBsAg = hepatitis B surface antigen; HCV = hepatitis C virus; HD = Huntington disease; MRI = magnetic resonance imaging; ObsROs = observer-reported outcomes; PerfOs = performance outcomes; PH = phone; PROs = patient-reported outcomes; RBR = Research Biosample Repository.

- ^a Post-observational follow-up visit will take place 2 weeks after end of observational period and will occur via clinic visit or by telephone call. Early termination visit should occur via clinic visit where possible.
- ^b Capacity to consent assessment (patient only) and informed consent (for both the patient and study companion [if available]).must be documented before any study-specific screening procedure is performed and may be obtained more than 28 days before baseline visit. A maximum of one re-screening will be allowed within 8 weeks of the initial screening failure for patients who fail the initial screening (e.g., as a consequence of abnormal laboratory values or general medical status not meeting inclusion or exclusion criteria). If re screening is required, central CAG repeat length testing from the initial screening does not need to be repeated, and the screening MRI and viral serology from the initial screening may be acceptable as part of the re screening assessments if performed within 12 weeks of the baseline visit.
- ^c Includes measurements of respiratory rate, pulse rate, and systolic and diastolic blood pressure while the patient is in a seated position after resting for approximately 5 minutes, and temperature. Record abnormalities observed at baseline on the General Medical History and Baseline Conditions eCRF.
- ^d Height in meters.
- ^e Weight in kilograms.
- ^f Includes evaluation of the head, eyes, ears, nose, and throat, and the cardiovascular, dermatologic, musculoskeletal, respiratory, gastrointestinal, genitourinary, and neurologic systems. Any abnormality identified at baseline should be recorded on the General Medical History and Baseline Conditions eCRF. Changes from baseline abnormalities should be recorded in patient notes. New or worsened clinically significant abnormalities associated with a study procedure should be recorded as adverse events on the Adverse Event eCFR.

Appendix 1 Schedule of Activities (cont.)

- ^g Neurological examination includes assessment of mental status, level of consciousness, sensory function, motor function, cranial nerve function and reflexes. Record abnormalities observed at baseline on the General Medical History and Baseline Conditions eCRF. New or worsened clinically significant abnormalities associated with a study procedure should be recorded as adverse events on the Adverse Event eCRF.
- ^h At screening, a mandatory whole blood sample will be obtained for DNA extraction for analysis of CAG repeat length.
- ⁱ Screening laboratory assessments include hematology (WBC count, RBC count, hemoglobin, hematocrit, platelet count, *all required*; differential count including neutrophils, eosinophils, basophils, monocytes, lymphocytes, other cells *as per local practice*); serum chemistry (sodium, potassium, chloride, bicarbonate, glucose, BUN or urea, creatinine, total protein, albumin, phosphorus, calcium, total and direct bilirubin, ALP, ALT, AST, uric acid, GGT, CPK, *as per local standard practice*); and urinalysis (dipstick including pH, specific gravity, glucose, protein, ketones, blood and microscopic examination, including sediment, RBCs, WBCs, casts, crystals, epithelial cells, bacteria, *as per local standard practice*). *Microscopic examination is only required in case of an abnormal dipstick result (for example, blood in urine or high protein value).*
- ^j Viral serology: HBsAg and HCV antibody.
- ^k All women of childbearing potential will have a serum pregnancy test at screening. Urine pregnancy tests will be performed at specified subsequent visits. If a urine pregnancy test is positive, it must be confirmed by a serum pregnancy test.
- ^l Coagulation: INR *and/or* PT, aPTT.
- ^m Patients will have CSF collected at baseline and at Months 3, 9, and 15 *for the assessment of RBC count, WBC count, glucose, and protein*. Prior to performing each scheduled lumbar puncture, local laboratory analysis of coagulation factors (INR *and/or* PT, aPTT) and platelets must be conducted and results reviewed. Collection for these local labs may occur at any time in the 72 hours prior to the lumbar puncture. The lumbar puncture should be performed at approximately the same time at each visit (ideally in the morning between 08:00 and 12:00 hours) to minimize potential diurnal variation of CSF parameters. CSF fluid (20 mL) is to be collected for analyses using a standard lumbar puncture collection kit. If there are difficulties in collecting 20 mL of CSF fluid, a minimum of 15 mL should be collected. A 24G Whitacre (atraumatic) needle should be used. Depending on institutional guidelines, local anesthesia may be used for the procedure. Sedation *is not allowed*. Spinal ultrasound may be used for the lumbar puncture procedure if deemed necessary, but is not required. Ultrasound guidance may be used if attempts at lumbar puncture without imaging are unsuccessful, if it is local practice to use ultrasound, *or if institutional guidelines dictate use of ultrasound with each lumbar puncture*. *In the case of a failed CSF collection procedure due to inadequate establishment of access to the IT space, a second attempt may occur up to 14 days after the originally attempt. For this additional visit, local laboratory analysis of coagulation factors (INR *and/or* PT, aPTT) and platelets must be conducted and the results reviewed, within 72 hours prior to performing the LP. In addition, neurological examination, vital signs and a review of AEs and concomitant medication should occur as part of the safety and tolerability evaluations on the day of LP.*

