4.1.2 Exclusion Criteria

Patients who meet any of the following criteria will be excluded from study entry:

- Any condition, including severe chorea, that would prevent either writing or performing pen-and-paper or smartphone-based tasks
- History of attempted suicide or suicidal ideation with plan (i.e., active suicidal ideation) that required hospital visit and/or change in level of care within 12 months prior to screening

Current active suicidal ideation is demonstrated by the Columbia-Suicide Severity Rating Scale (C-SSRS). If suicidal ideation is generally present, a risk assessment should be done by an appropriately qualified mental health professional to assess whether it is safe for the patient to participate in the study. Mild passive suicidal ideation (i.e., occasional thoughts that life is not worth living or is hard) without history of attempts or hospitalization over the past 12 months is generally acceptable for study participation, but final decision

on participation should be made carefully and in consultation with appropriately qualified mental health professional per judgment of the investigator.

- Current active psychosis, confusional state, or violent behavior
- Any serious medical condition or clinically significant laboratory, vital sign, or electrocardiogram abnormalities at screening that, in the investigator's judgement, precludes the patient's safe participation in and completion of the study
- Pregnant or breastfeeding, or intending to become pregnant during the study
- Positive for hepatitis C virus (HCV) antibody or hepatitis B surface antigen (HBsAg) at screening
- Known HIV infection
- Current or previous use of an antisense oligonucleotide (including small interfering RNA)
- Current use of antipsychotics prescribed for psychosis, cholinesterase inhibitors, memantine, amantadine, or riluzole including use within 12 weeks of enrollment

Use of antipsychotics for motor symptoms and/or tetrabenazine or deutetrabenazine is not permitted unless on stable dose for at least 12 weeks prior to screening.

- Treatment with an investigational drug within 30 days prior to screening or 5 half-lives of the investigational drug, whichever is longer
- Antiplatelet or anticoagulant therapy within the 14 days prior to screening or anticipated use during the study, including, but not limited, to aspirin (unless ≤ 81 mg/day), clopidogrel, dipyridamole, warfarin, dabigatran, rivaroxaban, and apixaban

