4.5.2 Informed Consent Forms and Screening Log

Written informed consent for participation in the study must be obtained before performing any study-related procedures (including screening evaluations). Informed Consent Forms for enrolled patients/study companions and for patients/study companions who are not subsequently enrolled will be maintained at the study site.

All screening evaluations must be completed and reviewed to confirm that patients meet eligibility criteria before enrollment. The investigator will maintain a screening log to record details of all patients screened and to confirm eligibility or record reasons for screening failure, as applicable.

A maximum of one re-screening will be allowed within 8 weeks of the initial screening failure for patients who fail the initial screening (e.g., as a consequence of abnormal laboratory values or general medical status not meeting inclusion or exclusion criteria). If re-screening is required, central CAG repeat length testing from the initial screening does not need to be repeated, and the screening MRI and viral serology from the initial screening may be acceptable as part of the re-screening assessments if performed within 12 weeks of the baseline visit. Participants are not required to re-sign the consent form if they are re-screened.

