4.5.3 Medical History, Concomitant Medication, and Demographic Data

Medical history, including clinically significant diseases, surgeries, cancer history (including prior cancer therapies and procedures), reproductive status, smoking history, and use of alcohol and drugs of abuse, will be recorded at baseline. In addition, all medications (e.g., prescription drugs, over-the-counter drugs, vaccines, herbal or homeopathic remedies, nutritional supplements) used by the patient from screening to the study completion/discontinuation visit will be recorded. At the time of each follow-up physical examination, an interval medical history should be obtained and any changes in medications, smoking, use of alcohol or drugs of abuse, any major procedures or hospitalizations, and any physician visits for HD or general medical care should be recorded.

Demographic data will include age, sex, and self-reported race/ethnicity and education level based upon International Standard Classification of Education scale. Demographic data and social status data (e.g., relationship to patient and employment status) will also be collected for the study companion.

A unique HD identification number (HDID) will be collected from patients who already have an HDID. For patients without an HDID who are willing to be assigned one, the number will be created via a web portal (see Section 8.4).

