4.5.6 Collection of Cerebrospinal Fluid (Lumbar Puncture Procedure)

Patients will have CSF collected at baseline and at Months 3, 9, and 15. Prior to performing each scheduled lumbar puncture, local laboratory analysis of coagulation factors (INR and/or PT, aPTT) and platelets must be conducted and results reviewed. Collection for these local labs may occur at any time in the 72 hours prior to the lumbar puncture. The lumbar puncture should be performed at approximately the same time at each visit (ideally in the morning between 08:00 and 12:00 hours) to minimize potential diurnal variation of CSF parameters. CSF fluid (20 mL) is to be collected for analyses using a standard lumbar puncture collection kit. If there are difficulties in collecting 20 mL of CSF fluid, a minimum of 15 mL should be collected. A 24G Whitacre (atraumatic) needle should be used. Depending on institutional guidelines, local anesthesia may be used for the procedure. Sedation *is not allowed*. Spinal ultrasound may be used for the lumbar puncture procedure if deemed necessary, but is not required. Ultrasound guidance may be used if attempts at lumbar puncture without imaging are unsuccessful, if it is local practice to use ultrasound, or if institutional guidelines dictate use of ultrasound with each lumbar puncture. *Fluoroscopy guidance can also be used, if local institutional guidelines dictate and if locally required approvals of the technique are obtained, but it is not required. Where fluoroscopy is used, patients should also be informed and consent obtained.*

If there is the occurrence of a failed CSF collection procedure due to inadequate establishment of access to the IT space, a second attempt may occur up to 14 days after the original attempt. For this additional visit, local laboratory analysis of coagulation factors (INR and/or PT, aPTT) and platelets must be conducted and the results reviewed, within 72 hours prior to performing the LP. In addition, neurological examination, vital signs and a review of AEs and concomitant medication should occur as part of the safety and tolerability evaluations on the day of LP.

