5.4.3 Reporting Requirements for Pregnancies

5.4.3.1 Pregnancies in Female Patients

Female patients of childbearing potential will be instructed to immediately inform the investigator if they become pregnant during the study. The investigator should then withdraw the patient from the study in the case of pregnancy. A paper Clinical Trial Pregnancy Reporting Form should be completed and submitted to the Sponsor or its designee immediately (i.e., no more than 24 hours after learning of the pregnancy), either by faxing or by scanning and emailing the form using the fax number or email address provided to investigators. Pregnancy should not be recorded on the Adverse Event eCRF. The investigator should counsel the patient and make referral to appropriate medical professional.

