Appendix 1 Schedule of Activities (cont.)

- ⁿ For MRI scans at Months 3, 9, and 15, the MRI should be scheduled to occur before the lumbar puncture. It can be scheduled in the days prior to the lumbar puncture (provided it occurs within the visit window), or it can be scheduled to occur on the same day as the lumbar puncture (provided it is prior to the lumbar puncture). *If re-scanning at a post-screening visit is necessary due to a non-usable original scan, the re-scanning should be conducted more than 3 days after the lumbar puncture and within one week of the original scan, if at all possible. If the rescan falls outside of the study visit window, this should be reported as a minor deviation.*
- ^o Questionnaires will be self-administered or administered by trained rater (as appropriate) at screening and at each clinic visit prior to the lumbar puncture. See [Appendix 2](#) and [Appendix 3](#) for details.
- ^p The C-SSRS must be administered on scheduled timepoints and may be performed at other timepoints per investigator's discretion.
- ^q The Roche HD mobile app includes a short, preconfigured schedule of daily tasks ("active test") that assess motor symptoms (upper and lower body movements, upper limb dexterity, voice) and non-motor symptoms (processing speed/voice). In addition, passive monitoring data is collected. During the in-clinic assessment, the entire suite of active tests should be performed.
- ^r Not applicable for a site that has not been granted approval for RBR sampling. Performed only for patients who have provided written informed consent to participate at participating sites.
- ^s At the time of each follow-up physical examination, an interval medical history should be obtained and any changes in medications, any major procedures or hospitalizations, and any physician visits for HD or general medical care should be recorded.
- ^t After informed consent has been obtained, adverse events caused by a protocol-mandated intervention should be reported until the patient's last visit or withdrawal. The investigator should follow each adverse event until the event has resolved to baseline grade or better, the event is assessed as stable by the investigator, the patient is lost to follow-up, or the patient withdraws consent. Every effort should be made to follow all serious adverse events considered to be related to protocol-related procedures until a final outcome can be reported.

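### Minor safety improvement: Baseline is the only scheduled lumbar puncture visit without a pregnancy test, so the first puncture rests on a screening result 1 to 29 days old

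*Protocol*

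**What the plan says.** Footnote k to Protocol Appendix 1, and Section 4.5.7 in the same terms, state: "All women of childbearing potential will have a serum pregnancy test at screening. Urine pregnancy tests will be performed at specified subsequent visits". A positive urine test must be confirmed in serum. The Appendix 1 row marks the test at Screening and Months 3, 9 and 15, and SAP Appendix 2 repeats the same row. Lumbar punctures are marked at Baseline and Months 3, 9 and 15.

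Other provisions bear on the same risk:

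- Section 4.1.2 excludes women who are "Pregnant or breastfeeding, or intending to become pregnant during the study".
- Section 4.5.3 has "reproductive status, smoking history, and use of alcohol and drugs of abuse, will be recorded at baseline".
- Section 5.4.3.1 says: "Female patients of childbearing potential will be instructed to immediately inform the investigator if they become pregnant during the study". The investigator should then withdraw her.
- Section 4.1.1 requires women of childbearing potential to agree to abstinence or acceptable contraception. The period named is the observational period.
- Section 4.5.6 allows imaging guidance for the puncture: "Fluoroscopy guidance can also be used, if local institutional guidelines dictate and if locally required approvals of the technique are obtained". It adds: "Where fluoroscopy is used, patients should also be informed and consent obtained". Footnote m, which covers the same procedure in the schedule, mentions ultrasound but not fluoroscopy.

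**The concern.** Pregnancy is an exclusion criterion and a ground for withdrawal, yet the schedule requires no check on the day of the first invasive study procedure. A pregnancy too early for the screening test to detect, or one that began during screening, could be unknown to both patient and site at the Baseline puncture. The woman would then have a puncture she should not have had and would be withdrawn later. At a site whose guidelines dictate fluoroscopy, there could also be radiation exposure, which is the one specific hazard that can be named from the documents.

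The protocol treats coagulation differently. Coagulation factors and platelets are tested at screening and again within 72 hours before each puncture, so for those a screening result is not considered enough.

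The issue is confined to patient safety. No study drug is given, and no endpoint, estimate or planned analysis depends on the test.

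**Working it through.** The documents give no figure for the age of the pregnancy test at the puncture, so there is none to reproduce. The check is a comparison of schedule rows followed by a count of days.

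**Schedule rows (Protocol Appendix 1)**

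| Row | Screening | Baseline | Month 3 | Month 9 | Month 15 |
|---|---|---|---|---|---|
| Pregnancy test | x | – | x | x | x |
| Lumbar puncture | – | x | x | x | x |
| MRI | x | – | x | x | x |
| Coagulation | x | x | x | x | x |
| Chemistry, hematology, urinalysis | x | x | x | x | x |

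Three things follow.

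- Baseline is the only puncture visit without a pregnancy test.
- The blank is not a fault of text extraction: neighbouring rows in the same table carry a Baseline mark, and the SAP schedule shows the same blank.
- The pregnancy-test row is identical to the MRI row. Footnote n gives the post-screening MRI visits: "For MRI scans at Months 3, 9, and 15, the MRI should be scheduled to occur before the lumbar puncture".

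**Age of the screening test at the Baseline puncture**

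Inputs: screening runs from Day -29 to Day -2 and Baseline from Day -1 to Day 1 (Appendix 1). There is no Day 0 (SAP Section 4).

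Age = day of puncture minus day of test, less 1 when the interval crosses from negative to positive days.

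- Puncture on Day -1: from -1 - (-2) = 1 day to -1 - (-29) = 28 days.
- Puncture on Day 1: from 1 - (-2) - 1 = 2 days to 1 - (-29) - 1 = 29 days.
- Overall range: 1 to 29 days. If a Day 0 were counted, the maximum would be 30.

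**Re-screening.** Section 4.5.2 lets a site carry forward the CAG result, and "the screening MRI and viral serology from the initial screening may be acceptable as part of the re-screening assessments if performed within 12 weeks". The pregnancy test is not among the results that may be reused, so re-screening does not lengthen the range.

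**Repeat of a failed Baseline puncture.** Section 4.5.6 and footnote m allow a second attempt up to 14 days later. They list coagulation, platelets, neurological examination, vital signs, adverse events and concomitant medication, but no pregnancy test. The extreme is 29 + 14 = 43 days. It needs a test on Day -29, a failed puncture on Day 1 and a repeat on the last permitted day.

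**After the fix.** A test at the Baseline visit, before the puncture, would be 0 days old on the same day, or 1 - (-1) - 1 = 1 day old if taken on Day -1 for a Day 1 puncture.

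**What the other safeguards can do.** The exclusion is backed by one required test, at screening. History and self-report depend on the woman knowing that she is pregnant. The contraception agreement is preventive and, as worded, starts with the observational period. Appendix 1 places Baseline in that period and lists screening separately, so screening itself is not formally covered.

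**Not available.** The documents do not give the share of women of childbearing potential, the use of fluoroscopy or the rate of failed punctures, so no expected number of affected women can be calculated.

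**The case against.** The best defence is that nothing in the protocol makes a pregnancy test a condition of lumbar puncture at any visit. The stated pre-puncture requirements are coagulation and platelets. The test visits match the MRI visits exactly, which suggests a deliberate rule. A reader might infer that the blank is a clerical slip or a breach of the protocol's own rule. The documents support neither reading, because the footnote requires urine tests only at visits the schedule specifies and Baseline is not one of them.

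A reader might also infer that pregnant women would be exposed to radiation unchecked. That cannot be shown. Fluoroscopy is confined to sites whose guidelines dictate it, with local approvals and patient consent, and those local rules may already require a pregnancy test. The documents do not say.

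Nor should 43 days be read as the usual age of the result. It stacks three worst cases, and its last 14 days fall in the observational period, when contraception has been agreed. Medical history and a complete physical examination at Baseline add some further protection.

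All of this stands, and it limits the point to a suggestion. It does not remove the gap: none of these measures reliably detects an unrecognised pregnancy, and an MRI-based reason for the test visits would not cover the Baseline puncture.

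**Conclusion.** The point holds as a cheap improvement, not as an error. The only required pregnancy result before the first puncture is 1 to 29 days old, whereas every later scheduled puncture visit includes a test. The range assumes that screening and Baseline take place within the Appendix 1 windows and that there is no Day 0. Counting a Day 0 would add one day to the maximum.

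The consequence is minor and limited to patient safety. The number of women affected is unknown and probably small, and sites remain free to test at Baseline without being told to. Because the remedy costs so little, it is worth considering.

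**What to change.** Mark a urine pregnancy test for women of childbearing potential in the Baseline column of the Appendix 1 pregnancy-test row. State that the result must be available before the puncture. A positive result would go to serum confirmation, as footnote k already requires.

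Urinalysis is already scheduled at Baseline, so the same sample can serve if it is collected before the puncture. The protocol does not fix that order, so some sites may have to collect urine earlier in the day.

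Optionally, add a sentence to Section 4.5.6 and footnote m requiring a current negative test before any fluoroscopy-guided puncture, including a repeat attempt, unless local rules already require it. At Months 3, 9 and 15 the urine test already scheduled would serve if done first. Universal testing at repeat punctures after Baseline is not needed.

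The cost is one mark in the schedule and, if the option is taken, one sentence in two places. In conduct it is at most about 100 Baseline urine tests, since up to approximately 100 patients of both sexes are to be enrolled. A fluoroscopy-guided repeat may need one extra urine sample, and a positive urine test would delay the puncture briefly for serum confirmation.
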